Neutrophil Extracellular Trap Formation in Newborn Infants at Risk for Inflammatory Syndromes

Protocol v 1, 1/15/2019

PI: [name]

IRB# 119244

Background

Dysregulation of acute inflammation contributes to the pathogenesis of many neonatal and pediatric diseases including sepsis, acute respiratory distress syndrome (ARDS), neonatal chronic lung disease (nCLD), retinopathy of prematurity (ROP), and necrotizing enterocolitis (NEC).

nCLD causes significant morbidity and mortality in the United States. nCLD is a complication of preterm birth that results from prolonged mechanical ventilation required for chronic respiratory failure. It occurs in 30 - 50% of mechanically ventilated extremely low birthweight infants (ELBW) with respiratory distress. While surfactant therapy and pre- or postnatal steroids have decreased the severity of nCLD, this significant morbidity associated with preterm birth remains common in at – risk infants, with about 8,000 to 10,000 new cases occurring annually in the US. The mortality rate due to nCLD in ELBW infants remains high from 15 - 40%. Furthermore, nCLD remains the most common cause of long-term hospitalization in neonates and is also associated with developmental delay. Whether or not dysregulated NET formation contributes to the pathogenesis of nCLD remains unknown.

ROP is the most common cause of pediatric blindness. Dysregulated inflammation is also implicated in the pathogenesis of ROP leading to retinal detachment and blindness. To date, no one has determined whether dysregulated NET formation contributes to ROP.

NEC, predominantly a disease of premature infants, afflicts $\approx 5 - 10\%$ of very low birth weight infants (< 1500 grams), develops typically in the 3rd to 4th week of life and often results in mortality. Infants born closer to term rarely develop NEC but those that do typically exhibit other risk factors such as ductal-dependent congenital heart disease or mesenteric ischemia. For these patients, NEC occurs typically in the first week of life and can prove fatal. Other sequelae of NEC include intestinal perforation, short gut syndrome, prolonged total parenteral nutrition with possible concomitant liver failure and a prolonged intensive care unit stay. While the etiology remains unknown, risk factors of prematurity, enteral feeds, infection and intestinal ischemia predict an increased risk for NEC⁵.

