The final common pathogenic pathway for NEC appears to depend on a dysregulated, pro-inflammatory response to bacterial translocation across an immature or damaged gastrointestinal epithelial barrier. Animal and human studies of NEC pathogenesis implicate inflammatory cytokines and phospholipids such as tumor necrosis factor alpha, Interleukin-8 and platelet activating factor (PAF). One animal model also demonstrated that aortic lipopolysaccharide (LPS) infusion caused a NEC-like syndrome in rats ⁶. Each of these biologically active inflammatory mediators activates the polymorphonuclear leukocyte (PMN)⁷, the primary effector cell of the acute inflammatory response to tissue injury or infection.

Data from animal models suggest a prominent role of the PMN in the pathogenesis of NEC. Musemeche et al. induced NEC-like disease in rats by intra-aortic injection of PAF⁸. They then used vinblastine, a chemotherapeutic agent, to induce neutropenia in rats four days prior to intra-aortic injection of PAF. The vinblastine-induced neutropenia protected against the clinical and pathologic manifestations of NEC-like disease.

The role of the human PMN in the acute inflammatory response is well documented. PMNs play a fundamental role in the innate immune response and are rapidly recruited to areas of injury or inflammation where they participate in bacterial phagocytosis and killing. Disorders associated with a deficiency or impairment of PMN function (neutropenia, chronic granulomatous disease (CGD), leukocyte adhesion deficiency) predispose to infections with gram-negative and gram-positive bacteria⁹. However, regulation of this potent component of the acute inflammatory response is imperative. Disorders such as ARDS, ischemia/reperfusion injury, and rheumatoid arthritis appear to result from the dysregulation of the PMNs' acute inflammatory response.

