Using data generated from the previous version of this IRB application (IRB_00039621 – Neutrophil Extracellular Trap Formation in Newborn Infants at Risk for Necrotizing Enterocolitis – Closed on 11/8/2018), we recently discovered a new regulatory mechanism governing NET formation in the first 2 weeks following birth for neonates, whether term or preterm. Using cord blood samples as well as samples of peripheral blood taken serially from neonates over the first 2 months of life, we recently identified a family of NET-Inhibitory Peptides (NIPs) which circulate in the fetus and neonate and potently inhibit PMNs from forming NETs. These NIPs inhibit NET formation despite stimulation with many NET-generating agonists like LPS, PMA, live gram+ or gram- bacteria, heme, or viruses. We further examined the use of these NIPs in the setting of in vivo sepsis. We found that pretreatment with the NIPs increased survival in the cecal ligation and puncture model of polymicrobial sepsis by 40-60%, with the survival advantage most likely due to decreased NET-mediated inflammatory tissue damage. With these published results (Yost CC, et al., JCI 2016), we are now funded by the NIH to evaluate the use of NIPs as therapeutic agents in preclinical models of neonatal sepsis. These studies will determine regulatory pathways governing NIP expression in the fetus and newborn, NIP mechanism of action, and efficacy in neonatal sepsis.

We hypothesize that NET formation contributes to the pathogenesis of inflammatory syndromes associated with sequelae of prematurity including sepsis, nCLD, ROP, and NEC by inappropriately releasing degradative proteins and tissue destructive enzymes into the inflammatory milieu of the premature infant. We further hypothesize that NIPs may provide protection against NET-associated inflammatory tissue damage.

Study Purposes and Objectives:

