The following study is best described as a prospective, in vitro longitudinal cellular biology study of LPS/PAFstimulated PMNs isolated from the cord and peripheral blood of premature infants at risk for inflammatory sequelae associated with prematurity (including neonatal Chronic Lung Disease (nCLD), early and late onset sepsis, necrotizing enterocolitis (NEC), and retinopathy of prematurity), and from term infants not considered at risk for such sequelae. In the specific case of NEC, we will also assay for NET formation in gastrointestinal tissue samples obtained at the time of surgery for severe NEC in enrolled prematurely born infants if that occurs. Such tissue samples will not be collected for other inflammatory syndromes of prematurity.

These studies are the first of their kind and aim to answer important questions such as the impact of dysregulated NET formation in the pathogenesis of these inflammatory sequelae of prematurity, the regulatory mechanisms

governing NET formation in newborn infants, the role of our newly discovered NET-Inhibitory Peptides (NIPs) as endogenous regulators of NET formation, and their potential use as novel therapeutic agents for dysregulated NET formation.

Inclusion Criteria:

Eligible Patients

1. Preterm infant patients delivered at UUMC and hospitalized in the NICU who are \leq 1500 grams or < 30 weeks gestational age at birth

Cord blood sample obtained at delivery

Peripheral blood sample obtained during IV start under anesthesia at any elective surgeries during the first year of life

2. Term infants delivered at UUMC without complication, either via cesarean section or vaginal delivery.

Cord blood sample obtained at delivery

Heel-prick blood sample obtained at 24 hours of life

Exclusion criteria:

None

Study Procedures:

Recruitment: We will screen charts through a waiver of authorization for potential participants within the University of Utah covered entity. Eligible participants identified through the waiver of authorization will be identified once they are admitted to the hospital for clinical management, with the expectation of delivery during the current hospital admission.

Inclusion/exclusion criteria will be reviewed with the patient's chart and then approached once initial eligibility criteria have been verified.

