After delivery, cord blood will be drawn from the ligated umbilical cord and placenta. For premature deliveries of infants weighing less than 1500 grams, it is estimated that only 5 – 10 mL of cord blood will be obtained. The resuscitation and treatment of a premature infant often requires cord blood specimens for such clinical tests as arterial and venous cord blood gases and blood type and crossmatch in preparation for probable future blood transfusions. These specific clinical cord blood samples will be collected before study blood collection. The residual cord blood will be dripped into sterile 8 mL EDTA-anticoagulated vacutainers, labeled with a study generated patient identifier and transported by [name] or his laboratory technicians to his lab in the Eccles Institute of Genetics for immediate PMN isolation and sample stabilization. This rapid isolation and sample stabilization is necessary given the short life of PMNs *in vitro* and the potential for PMN activation after isolation.

The family will then be approached regarding informed consent as discussed below. If informed consent is obtained, preparations will be made to obtain 3 serial 0.5 ml samples of peripheral blood during the infant's NICU stay. Samples will be collected on the routine lab draw day that most closely correlates with the following days of life (DOL) #: 3, 7, and 14 if still in the NICU at either UUMC or PCH.

Longitudinal samples will be collected into a 0.5 ml EDTA-anticoagulated microtainers and processed in an identical manner to the cord blood already collected. These serial samples will only be collected during routine clinical laboratory draws occurring around the scheduled DOL. No new lines, IVs or heel stick wounds will be started or made for the sole purpose of drawing the scheduled study sample.

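### Preterm serial samples are timed by day of life only, with no record of sepsis onset, so samples taken before and after sepsis begins may be analysed together and a NET-sepsis association could be a result of illness

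*Combined protocol and SAP*

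**What the plan says.** The causal aim is in the Background: "We hypothesize that NET formation contributes to the pathogenesis of inflammatory syndromes associated with sequelae of prematurity including sepsis, nCLD, ROP, and NEC". Study Purposes and Objectives describes a prospective longitudinal study whose target conditions include "early and late onset sepsis, necrotizing enterocolitis (NEC), and retinopathy of prematurity".

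Timing is set in Study Procedures, Phlebotomy, Patient Group #1. After cord blood at delivery, three small peripheral samples are taken on the routine laboratory day nearest "the following days of life (DOL) #: 3, 7, and 14 if still in the NICU at either UUMC or PCH". The same section adds: "These serial samples will only be collected during routine clinical laboratory draws occurring around the scheduled DOL". Nothing ties a draw to the start of an illness.

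There are no exclusion criteria, so an infant who becomes septic stays in the serial sampling. Data Analysis gives one-way ANOVA with Holm-Sidak comparisons for extracellular DNA and NE activity. It names no grouping factor, no comparison by disease status and no treatment of repeated samples. No section defines sepsis or NEC, collects an onset date, or says how samples taken during or after illness are handled.

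**The concern.** The hypothesis runs from NETs to disease. A longitudinal design can support it mainly through time order, by showing that NET formation differed before the illness. The Background itself supplies a route in the other direction. Of the inflammatory mediators implicated in NEC it says: "Each of these biologically active inflammatory mediators activates the polymorphonuclear leukocyte". A neutrophil collected during or after an inflammatory illness may therefore behave differently because of that illness.

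Early and late onset sepsis are both named targets, and onset can fall before or between the scheduled days. If samples from both sides of onset are analysed together, a difference between septic and non-septic infants cannot be read as a contribution of NETs to sepsis. Without an onset date in the dataset, the two explanations cannot be separated afterwards.

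**Working it through.** The plan gives no figure to reproduce on this point. The enrolment of 40 preterm and 20 term infants comes without alpha, power, effect size or SD.

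**Step 1: samples at or after onset, from the schedule alone.** The scheduled days are 3, 7 and 14. A sample is at or after onset if its day is equal to or later than the onset day.

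| Onset | Samples at or after onset | Peripheral samples before onset |
|---|---|---|
| by DOL 3 | 3 of 3 | none |
| DOL 4-7 | 2 of 3 | DOL 3 |
| DOL 8-14 | 1 of 3 | DOL 3, 7 |
| DOL 15 or later | 0 of 3 | DOL 3, 7, 14 |

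Cord blood precedes any onset after birth. Actual draws follow the nearest routine day, so an individual infant can move by a row.

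**Step 2: NEC.** For very low birth weight infants the Background says NEC "develops typically in the 3rd to 4th week of life and often results in mortality", about DOL 15-28 if birth is DOL 1. That is the last row of the table. Only unusually early NEC is affected, or a DOL 14 draw at the edge of the window (birth counted as DOL 0, or a late draw). At the Background's rate of about 5-10%, expected cases among 40 infants are 40 × 0.05 = 2 to 40 × 0.10 = 4.

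**Step 3: illustration of size for sepsis.** Every input except the 40 infants and the three sampling days is an assumption: the share with sepsis, the spread of onset, a within-infant correlation of 0.5, and the shift after onset. NETs have no causal effect. Each infant's mean over three samples is compared between septic and non-septic infants by a two-sample t-test at 5%. The plan does not state this test; it stands in for any analysis that merges the days.

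Expected spurious difference = shift × mean share of samples at or after onset.

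- Onset even over the four rows: share = (1 + 2/3 + 1/3 + 0)/4 = 0.50.
- Onset uniform over DOL 4-14 (4 days with 2 samples, 7 days with 1): share = (4×2 + 7×1)/(11×3) = 15/33 = 0.45.
- Later onset, 10/20/30/40% over the four rows: share = 0.10 + 0.20×2/3 + 0.30×1/3 = 0.33.

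| Onset pattern | Infants septic | Shift 0.5 SD: difference, false-positive rate | Shift 1.0 SD: difference, false-positive rate |
|---|---|---|---|
| Even | 30% | 0.25 SD, 14% | 0.50 SD, 39% |
| DOL 4-14 | 30% | 0.23 SD, 13% | 0.45 SD, 35% |
| DOL 4-14 | 20% | 0.23 SD, 10% | 0.45 SD, 28% |
| DOL 4-14 | 10% | 0.23 SD, 7.5% | 0.45 SD, 18% |
| Later | 30% | 0.17 SD, 9% | 0.33 SD, 21% |

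Differences are from the formula; the simulated ones agree to within about 0.01 SD. Rates are simulated. A fall of the same size after onset gives the same rates with the sign reversed. Milder inputs lie closer to 5%.

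**Step 4: effect of restricting to pre-onset samples.** With onset over DOL 4-14, the difference becomes -0.01 to 0.01 SD and the false-positive rate 6-7.5%. The small excess over 5% arises because cases contribute fewer samples and so have more variable means. With onset at DOL 15-28, using all samples gives 4.5-5.2%, which confirms Step 2.

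**The case against.** The best defence is that the plan nowhere says samples before and after onset will be combined. A reader might infer pooling from the one-way ANOVA, but its factor is unnamed and no averaging over days is written. The draws have nominal days, so a day-by-day analysis remains possible. This stands, and the supportable wording is that samples may be analysed together. It does not remove the problem. A day-by-day analysis would still mix ill and well infants at each DOL, and without onset dates nobody could separate them.

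Four further readings are tempting and are not supported:

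- **NEC is equally affected.** The Background places typical NEC after DOL 14. Its remark on first-week NEC concerns infants born closer to term, who are not in the serially sampled group. NEC surgical tissue is taken after onset but is assessed separately and qualitatively.
- **The bias has a known direction.** The remark on neutrophil activation concerns NEC mediators. The outcome here is NET formation after isolated cells are stimulated in the laboratory, and the documents do not say whether earlier activation in the infant raises or lowers that response. The Background also reports circulating inhibitory peptides in the newborn.
- **A normal-maturation result is contaminated.** The Background calls the timing of maturation unknown, but no such analysis is written.
- **The trial's false-positive rate is up to 39%.** That figure rests on assumed inputs and on a test the plan does not name.

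It is also fair to say that this gap sits beneath a larger one: no disease outcome or disease-status comparison is defined. Onset flags become useful only once those exist.

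**Conclusion.** The concern holds for sepsis beginning in the first two weeks. The firm part needs only the sampling schedule: one to three of the three peripheral samples then fall at or after onset and cannot support a NETs-to-disease reading. The plan has neither the data nor a rule to set them apart. Typical NEC is outside the problem.

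The size is illustrative. With 10-30% of 40 infants septic, a correlation of 0.5 and a shift of 0.5-1.0 SD, the spurious difference is roughly 0.2-0.5 SD and the false-positive rate runs from about 8% to about 39% in the settings shown. A shift downwards could instead hide a true association. The plan should be changed on this point, because its pathogenesis aim depends on time order.

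**What to change.** 1. Define sepsis and NEC, and record from the chart the date and time of first clinical onset.
2. Flag every sample as before, or at or after, onset.
3. Base any statement that NETs or NIPs contribute to disease on cord blood and pre-onset samples. Compare them with infants still disease-free at the same DOL, since the Background describes NET regulation particular to the first two weeks after birth. Where an infant contributes several samples, use a model with an infant-level random effect.
4. Report samples at or after onset separately, as response to illness.
5. Repeat any comparison across DOL without those samples.

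The cost is one chart date and time per event and one analysis flag, with no extra blood or procedures. The real price is precision. Few cases will have pre-onset peripheral samples, and sepsis starting by DOL 3 will have cord blood only. Estimates will be imprecise and should be presented as exploratory.

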For the small subset of at-risk infants who develop NEC requiring surgery at PCH, whether born at UUMC or transported to PCH from a referring institution, we will also obtain fixed and paraffin-embedded gastrointestinal tissue samples at the time of surgery for analysis of NET formation. These samples will be obtained by the pediatric surgical team at the time of exploratory laparotomy and processed by the diagnostic pathology service at PCH. For those infants transported to PCH with surgical NEC from referring institutions, informed consent will be requested upon admission to PCH NICU. If informed consent is obtained, the samples would be processed and transferred by [name] to his laboratory for further analysis.

Patient Group #2: Healthy term infants born at UUMC

After delivery, cord blood will be drawn from the ligated umbilical cord and placenta. For term deliveries at UUMC, it is estimated that approximately 15 - 25 mL of cord blood can be routinely obtained without compromising needs for possible clinical studies such as infant blood-typing. Samples will be dripped into sterile 8

mL EDTA-anticoagulated vacutainers, labeled with a study generated patient identifier and transported by [name] or his laboratory technicians to his lab in the Eccles Institute of Human Genetics for immediate PMN isolation and sample stabilization. Again, this rapid isolation and sample stabilization is necessary given the short life of PMNs *in vitro* and the potential for PMN activation after isolation.

The family will then be approached regarding informed consent as discussed below. If informed consent is obtained, preparations will be made to obtain one additional 1 ml sample of peripheral blood during the infant's heel stick wounding for the 24-hour metabolic screening test performed on all infants before DOL #3 and before hospital discharge. The sample will be collected into 2 0.5 ml EDTA-anticoagulated microtainers and processed in an identical manner to the cord blood already collected. This additional sample will only be collected during the routine 24 – 48-hour metabolic screening laboratory draw. No new lines, IVs or heel stick wounds will be started or made for the sole purpose of drawing the scheduled study sample.

Experimental Procedures:

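### Does the plan leave it unsettled which peripheral blood samples are drawn from preterm infants?

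*Combined protocol and SAP*

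**What the plan says.** For preterm infants, the Inclusion Criteria section puts two specimens under the eligibility statement: cord blood at delivery, and a "Peripheral blood sample obtained during IV start under anesthesia at any elective surgeries during the first year of life". It gives no volume, tube or number for the second, and does not mention serial draws.

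Phlebotomy, Patient Group #1, describes cord blood and then says that, once consent is given, "preparations will be made to obtain 3 serial 0.5 ml samples of peripheral blood" during the NICU stay. The timing is the routine laboratory day nearest "days of life (DOL) #: 3, 7, and 14 if still in the NICU at either UUMC or PCH". It names the tube (0.5 mL EDTA microtainer), the processing (the same as for cord blood) and the restriction to routine clinical draws. It does not mention elective surgery.

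For term infants the two sections agree in substance. The Inclusion Criteria have cord blood and a "Heel-prick blood sample obtained at 24 hours of life". Phlebotomy, Patient Group #2, has cord blood and "one additional 1 ml sample of peripheral blood" at the routine metabolic screen.

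Study Purposes and Objectives calls the work "best described as a prospective, in vitro longitudinal cellular biology study". Data Analysis gives 40 preterm and 20 term infants and a one-way ANOVA with Holm-Sidak comparisons, without naming the groups or time points compared.

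**The concern.** The two preterm lists share cord blood and no peripheral sample. Because the term lists do correspond, a reader may take the Inclusion Criteria lists to be complete. On that reading the protocol contains two different preterm schedules and does not choose between them.

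If only the Inclusion Criteria applied, there would be no fixed-age peripheral blood and the longitudinal element would be lost. If only Phlebotomy applied, no preterm blood would be planned after about day 14, although the Background places typical NEC onset in the third to fourth week. If both applied, blood taken months after birth would sit beside a series covering the first two weeks, and an analyst might pool the two. For research blood from infants this small, one also expects the plan to say exactly what is drawn.

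**Working it through.** The documents give no figure to reproduce, so the check compares the lists and then counts samples.

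**1. The preterm lists side by side**

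| Item | Inclusion Criteria | Phlebotomy, Group #1 |
|---|---|---|
| Cord blood | yes | yes |
| Days 3, 7, 14 | not mentioned | yes, with number, volume, tube, processing and restriction |
| Elective surgery, first year | yes, no details | not mentioned |

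Shared items: 1. Shared peripheral items: 0. The mismatch is confirmed.

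**2. Do the lists exclude each other?** No. Neither says that its samples are the only ones. The rule confining collection to routine laboratory draws is written for the serial samples. The bar on new lines, IVs or heel sticks made solely for the study is also respected by the surgery draw, which uses an IV start already needed for anesthesia.

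**3. Which text governs the serial draws?** Phlebotomy falls under Study Procedures and tells staff what to do. The other list sits under an eligibility heading and could not be carried out on its own, since it has no volume or tube. The objectives also call the study longitudinal, which fits the serial draws and argues against reading the eligibility list as excluding them.

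**4. Sample counts**

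- Serial samples per infant: 3 × 0.5 mL = 1.5 mL.
- Serial samples overall: 3 × 40 = 120 at most, or 120 × 0.5 mL = 60 mL. Fewer if infants leave the NICU.
- Surgery samples: S, not stated. Assuming 10% to 50% of infants have one such draw, S = 0.10 × 40 = 4 to 0.50 × 40 = 20.
- Both lists together: 120 + S, or 124 to 140 under that assumption.

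The realistic uncertainty is therefore 120 against 120 + S. A contrast of 0 against 120 arises only if staff disregard Phlebotomy.

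**5. Is stopping the series at about day 14 a fault?** No. The Background reports, from the predecessor study, "a new regulatory mechanism governing NET formation in the first 2 weeks following birth", and says that study used "samples of peripheral blood taken serially from neonates over the first 2 months of life". A series ending near day 14 covers the window the investigators want to examine.

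**The case for a change.** The strongest case for a change is that the wording is deficient on every reading. If the lists add up, each is incomplete: the surgery sample lacks the volume and tube that Phlebotomy gives for every other peripheral sample, and the eligibility list omits the core draws. If they do not add up, one scheme must go and the plan does not say which. The agreement between the term lists suggests that the format was meant to be complete. A single reconciled list would cost only wording, with perhaps an administrative amendment.

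Part of this stands. The surgery sample has no procedure, and one list would read better. The rest is weaker.

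- The term agreement is a single instance and is not exact in timing: one section says 24 hours, while the other also describes a 24 to 48-hour screen. That fits a shorthand summary better than an exhaustive schedule.
- The pooling risk is hypothetical. No section places surgery blood in the day 3 to 14 series, and the age gap would be plain to any analyst.
- The NEC timing point has little to act on. Data Analysis names no NEC comparison. If the Background's 5 to 10% incidence for very low birth weight infants applied to this group, 40 infants would yield about 0.05 × 40 = 2 to 0.10 × 40 = 4 cases. The tissue from NEC surgery is already assessed separately and qualitatively.

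**Conclusion.** No change to the plan follows. The Inclusion Criteria and Phlebotomy sections are unreconciled but compatible, and following both as written gives cord blood, up to 120 serial samples and an opportunistic surgery sample where one arises. The only open matter is whether and how that last sample is collected: an unstated number, 4 to 20 if 10% to 50% of infants contribute one each. It is additional to the scheduled series, and no stated analysis is shown to rest on it.

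This conclusion assumes that staff work from the procedure section when drawing blood, and that analysts keep samples of very different ages apart. Both are ordinary practice. Writing one list would record what is intended, but it would not alter the serial draws or the stated comparison.

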Plasma samples will be obtained from whole blood samples via centrifugation. The aliquots of the plasma will then be run on Tris-Tricine precast gels to resolve proteins and peptides with a molecular weight between 1 and 30 kD. A standard curve with increasing concentration of synthesized NIPs will be run on the same gel and concentration will be determined by comparing the fluorescent intensity of the plasma band to those of the standard curve. Alternatively, we are developing a HPLC/MS2 assay which will use a synthesized "heavy" variant of NIPs to quantify NIP concentration in plasma compared to a known amount of spiked "heavy" NIP.

Qualitative assessment of NET formation in NEC tissue specimens via immunohistochemistry:

NEC tissue specimens processed by pediatric pathology at PCMC and embedded in paraffin will be transported to [name] laboratory and analyzed for NET formation via immunofluorescence. Surgical samples will be sectioned at $5 - 10 \,\mu$ m thickness. NETs will be visualized by examining the colocalization of antibodies against DNA, histones, and neutrophil elastase.

Data Analysis:

NET formation as assessed qualitatively via live cell imaging and immunohistochemistry and quantitatively via extracellular DNA quantitation and neutrophil elastase activity assays.

We anticipate enrolling 40 prematurely born infants in patient group # 1, 20 healthy term newborn infants in patient group # 2 during this study.

Statistical comparisons for the quantitative assays of extracellular DNA and NE activity will be made via one-way ANOVA with post hoc Pairwise Multiple Comparisons made via the Holm-Sidak method.

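### Which preterm infants supply the DOL 3, 7 and 14 samples depends on their clinical course, so an age comparison may partly reflect who was sampled, in an unknown direction

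*Combined protocol and SAP*

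**What the plan says.** Under Study Procedures, Phlebotomy, Patient Group #1, three 0.5 mL peripheral samples are planned for each consented preterm infant, at "days of life (DOL) #: 3, 7, and 14 if still in the NICU at either UUMC or PCH". The timing is flexible: "Samples will be collected on the routine lab draw day that most closely correlates with the following days of life". Collection depends on clinical need: "These serial samples will only be collected during routine clinical laboratory draws occurring around the scheduled DOL". The same section adds: "No new lines, IVs or heel stick wounds will be started or made for the sole purpose of drawing the scheduled study sample". No sampling window is given.

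Eligibility (Inclusion Criteria) is a birth weight at or below, or a gestation under, the limits in "1500 grams or < 30 weeks gestational age at birth". An infant can therefore qualify on weight alone at a later gestation. The same section lists one later sample: "Peripheral blood sample obtained during IV start under anesthesia at any elective surgeries during the first year of life".

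Data Analysis states: "We anticipate enrolling 40 prematurely born infants in patient group # 1". It compares the quantitative assays by one-way ANOVA followed by Holm-Sidak pairwise comparisons. It does not name the groups to be compared. It gives no infant term, covariate, expected missingness or missing-data method, and the protocol makes no provision for recording why a sample was missed.

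**The concern.** Whether an infant stays in the two NICUs, and whether blood is being drawn anyway, both follow from how that infant is doing. Who is present at DOL 14 is thus partly decided by illness.

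The study's own hypothesis links NET formation to inflammatory illness, so the outcome may be tied to the process that decides who is sampled. Change with age is also central. The protocol calls the study longitudinal, Background says it is not known when newborn neutrophils mature in this respect, and it describes a regulatory mechanism acting in the first two weeks. DOL 14 is the end of that period.

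If the ages are compared as independent groups, a cord-to-DOL 14 difference could be maturation, a change in the set of infants, or both. The plan has no means of telling these apart.

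**Working it through.** The plan states no power, effect size, SD or loss rate, so there is no figure to reproduce. The calculations below are illustrative. Every loss rate, correlation and sick-well difference in them is assumed.

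**1. Shift in the DOL 14 mean when well infants are lost.** Assume no true age effect, NET output correlated r = 0.3 or 0.5 with a standard normal illness score, and a fraction m without a DOL 14 sample.

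*Extreme case: exactly the least ill are lost.* Shift = r × φ(z_m)/(1 − m), where z_m is the m-quantile of the standard normal.

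| m | φ(z_m)/(1 − m) | r = 0.3 | r = 0.5 |
|---|---|---|---|
| 0.05 | 0.109 | 0.03 SD | 0.05 SD |
| 0.10 | 0.195 | 0.06 SD | 0.10 SD |
| 0.20 | 0.350 | 0.10 SD | 0.17 SD |
| 0.30 | 0.497 | 0.15 SD | 0.25 SD |
| 0.40 | 0.644 | 0.19 SD | 0.32 SD |

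*Graded case: the odds of being sampled rise 2- to 3-fold per SD of illness.* With m = 0.2 to 0.4 the shift is 0.04 to 0.18 SD, and sampled and unsampled infants differ by 0.19 to 0.46 SD. With m = 0.05 to 0.10 the shift is 0.01 to 0.05 SD.

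**2. Does the sign hold if sick infants are lost?** Let s be the sick share at enrolment, r_s and r_w the probabilities that sick and well infants are sampled, and δ the sick-well difference. The sick share among those sampled is s' = s·r_s/[s·r_s + (1 − s)·r_w], and the shift is δ(s' − s). With δ = 1 SD:

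| s | r_s | r_w | s' | Shift |
|---|---|---|---|---|
| 0.3 | 1 | 0.80 | 0.349 | +0.05 SD |
| 0.3 | 1 | 0.50 | 0.462 | +0.16 SD |
| 0.5 | 1 | 0.50 | 0.667 | +0.17 SD |
| 0.3 | 0.85 | 0.85 | 0.300 | 0 |
| 0.3 | 0.85 | 1 | 0.267 | −0.03 SD |
| 0.5 | 0.85 | 1 | 0.459 | −0.04 SD |
| 0.5 | 0.60 | 1 | 0.375 | −0.13 SD |

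The sign reverses with the reason for loss.

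**3. What a within-infant contrast removes.** Under the model in step 1, write r_cord and r_14 for the correlations of NET output with illness at the two ages. Among infants with both samples, the bias in the paired change is (r_14 − r_cord) × φ(z_m)/(1 − m). If the illness effect is the same at both ages, this is zero. If illness arises after birth, so that r_cord = 0, all of it remains: with m = 0.2 and r_14 = 0.3 it is 0.3 × 0.350 = 0.10 SD.

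**4. Scale.** With 40 cord samples against 24 to 32 at DOL 14 (losses of 40% to 20%), the detectable difference is 2.80 × √(1/40 + 1/24) = 0.72 SD to 2.80 × √(1/40 + 1/32) = 0.66 SD. This assumes 80% power, two-sided 0.05, independent groups and no multiplicity adjustment.

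**The case against.** The best case for leaving the plan alone is that little may be lost by DOL 14. An infant born before 30 weeks is then under 32 weeks postmenstrual age, so discharge home is probably uncommon (the documents give no discharge data). Movement between UUMC and PCH is already covered. Background places NEC in preterm infants typically in the third to fourth week, after the last serial sample. The graded shifts are small beside a detectable difference of about 0.7 SD. Sampling only at clinical draws is also a deliberate safeguard against study-only punctures. These points stand, and they limit the size of the problem. They do not settle it, because infants qualifying on weight alone may leave earlier and any infant may lack a draw, be transferred or die.

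A reader might infer more than the documents support in four places:

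- **That later samples over-represent sick infants.** Death, or transfer of sick infants, works the other way. Background cites high mortality from chronic lung disease in the smallest infants, though this is not a rate of death by DOL 14.
- **That a missing draw ends the series.** The nearest draw day is used, so one sample is shifted or skipped and later ones remain possible. Only leaving the two NICUs ends it.
- **That an infant leaving on DOL 10-12 certainly gives no DOL 14 sample.** The nearest-day rule and the condition "if still in the NICU at either UUMC or PCH" can be read either way.
- **That the cord group is nearly complete.** Cord samples are what remains after clinical tests, so this group may have gaps too.

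The elective-surgery sample does not replace a missed DOL 14 value, and it depends on needing surgery.

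**Conclusion.** The concern holds in a limited form. Sampling at DOL 3, 7 and 14 is conditional on NICU stay and clinical draws, and the planned ANOVA cannot separate age from a change in the infants sampled. The direction of any bias cannot be determined from the documents.

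If well infants are the ones lost, a 20-40% loss gives an upward shift of about 0.04-0.32 SD. The top of that range needs three extremes together: 40% missing, only the least ill lost, and r = 0.5. At 5-10% missing the shift is about 0.01-0.10 SD, and loss of sick infants makes it negative. No sample-size figure is affected. The change is still worth making, because it is cheap and reasons for missed samples are hard to reconstruct afterwards.

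**What to change.** 1. Make age contrasts within infant. Either restrict each contrast to infants with both samples, or fit a mixed model with infant as a random effect and actual age at sampling. The mixed model is needed if samples taken off schedule are to be used at their true age.
2. State in the Patient Group #1 section that, if departure is planned before a scheduled sample, that 0.5 mL sample is taken at the last clinically ordered draw before departure and analysed at its actual age. This also settles the ambiguity between the nearest-day rule and the NICU condition. It adds no punctures and stays within the planned 3 × 0.5 mL.
3. As supporting checks, log one reason for each missed sample (death, transfer or discharge, no clinical draw, technical), and tabulate cord NET and NIP values for infants with and without a DOL 14 sample.

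**Cost:** protocol wording, a revised analysis sentence, one log field and one table. Paired contrasts use fewer infants and describe only those retained, and some last samples will be earlier than DOL 14. None of this removes selection on illness arising after birth, and the cord-value table cannot detect it, so the report should say so.
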